2 STUDY DESCRIPTION

2.1 Study Design

C4951004 is a multicenter, Phase 4, randomized, double-blind placebo-controlled study, with an Open-Label Extension (OLE) Phase to assess the efficacy and tolerability of rimegepant for the acute treatment of migraine in subjects who are unsuitable for triptan use.

[figure not shown]
The study has 4 phases:

- Screening Phase: Lasts up to 28 days and includes the Screening Visit.
- DBT Phase:
 - Includes the Baseline Visit at which randomization occurs, and DBT EOT Visit.

- Subjects are randomized 1:1 to rimegepant orally dissolving tablet (ODT) 75 mg or matching placebo.
- Randomization is stratified using a Randomization and Trial Supply Management (RTSM) system by history of clinically relevant cardiovascular (CV) disease (yes or no). See Section 2.2.
- After randomization, 1 tablet of study medication is dispensed to subjects to take home for up to 45 days.
- Subjects are instructed by an electronic diary (eDiary) to take 1 tablet of study drug after a migraine attack of moderate or severe headache pain intensity.
- Subjects return to the study site for the DBT EOT Visit either (1) within 7 (\pm 2) days after taking study drug, or (2) within 45 days after randomization otherwise.
- OLE Phase:
 - Subjects who complete the DBT Phase and continue to meet all inclusion/exclusion criteria may enter the OLE Phase, pending review of laboratory test results at the DBT EOT Visit.
 - Subjects may take up to 1 tablet of open-label ODT rimegepant 75 mg per calendar day as needed for acute treatment of migraine for a maximum of 18 doses per month (month is 28 days).
 - Lasts up to 12 weeks, and includes the Week 2, Week 4, Week 8, Week 12, and OLE EOT Visits.
 - All subjects who discontinue early from the OLE Phase should complete the OLE EOT Visit. Otherwise, subjects should complete the Week 12 Visit.
- Follow-Up Phase
 - Lasts up to 2 weeks, and includes the Follow-Up Week 2 Visit primarily for safety assessments. This visit should occur approximately 2 weeks after the Week 12 or OLE EOT Visit.
 - All subjects who enter the OLE Phase should complete the Follow-Up Week 2 Visit (regardless of completing the OLE Phase), except those who discontinue early from the OLE Phase due to withdrawal by subject or lost to follow-up.

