5 SAMPLE SIZE, POWER, AND TYPE I ERROR

It is anticipated that about 90% of the 300 subjects randomized to each treatment group will have a migraine in the allotted time period of the DBT Phase, resulting in approximately 270 subjects evaluable for efficacy in each treatment group.

The sample size calculation is based on pooled results from Phase 3 single-dose migraine studies C4951054 (BHV3000-301), C4951055 (BHV3000-302), and C4951056 (BHV3000-303). Pooled response rates for migraine headache pain relief at 2 hours postdose were 57.9% for rimegepant 75 mg and 43.9% for placebo in these studies.

A total sample size of 540 evaluable subjects (270 per treatment group) will provide approximately 90% power for the primary endpoint of migraine headache pain relief at 2 hours postdose in the DBT Phase. This is based on a chi-square test with a 2-sided alpha level of 0.05, and assumes that the true response rates in the subjects unsuitable for triptan use is equivalent to the overall pooled response rates above.

Type 1 error is controlled using a 2-sided alpha level of 0.05 and hierarchical testing. First, the significance of the primary endpoint is evaluated at the 2-sided alpha level of 0.05 for rimegepant versus placebo. If the primary endpoint is not significant (i.e., $p\text{-value} > 0.05$), then any further tests on key secondary endpoints will have p-values presented only for descriptive purposes. If the primary endpoint is significant (i.e., $p\text{-value} \leq 0.05$), then the key secondary endpoints are tested hierarchically, each at a 2-sided alpha level of 0.05, in the order specified in Section 3.2.2.1. Thus, a key secondary endpoint is tested only if the preceding key secondary endpoint in the hierarchy is determined to be significant (i.e., $p\text{-value} \leq 0.05$). If a test in the hierarchy is not significant, then any further tests on endpoints in the sequence have p-values presented only for descriptive purposes, and no conclusions are drawn from those results.

For testing of other secondary or exploratory endpoints, no attempt is made to adjust for multiplicity. P-values are evaluated at an unadjusted, 2-sided alpha level of 0.05 and presented only for descriptive purposes.

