6.3 Efficacy

Efficacy endpoints are assessed by as-randomized treatment group.

Randomization is stratified using the RTSM system, but analyses use the imputed randomization stratum, which is based primarily on the actual data (i.e., history of clinically relevant CV disease; see Section 6.2.5.1). The rationale for using the actual data in analyses is that sites may erroneously report the wrong stratum in the RTSM system. Hence, treatment group comparisons of binary efficacy endpoints are stratified by the imputed randomization stratum except within subgroups. If there are sparse data within a stratum, then results may be presented unstratified. Note that the phrase “randomization stratum” refers to the imputed randomization stratum throughout this section.

For binary efficacy endpoints, CIs are based on a normal approximation to the binomial distribution using asymptotic standard error (ASE). For continuous efficacy endpoints, CIs are based on the normal distribution. All CIs are 2-sided.

See Sections 7.2 and 7.3 for the definition of efficacy analysis periods and study days.

Efficacy Endpoints During the DBT Phase

During the DBT Phase, select endpoints are assessed over time at all scheduled time points postdose: 15, 30, 45, 60, and 90 minutes; 2, 3, 4, 6, 8, 24, and 48 hours.

Analyses are based on the DBT efficacy analysis set with eDiary measurement dates in the DBT Phase analysis period at planned time points of 15 minutes through 48 hours from the eDiary Migraine question category (see Section 7.4.2).

Efficacy Endpoints During the OLE Phase

Analyses are based on the OLE migraine analysis set with eDiary measurement dates in the OLE Phase analysis period from the eDiary Migraine question category (see Section 7.4.2).

Methods of Handling Missing Data

Methods of handling missing data in analyses of binary efficacy endpoints during the DBT Phase are defined as follows:

- Noncompleter = Failure (NC=F): Subjects with missing data at a single time point are classified as failures. This missing data imputation method is applied to endpoints based on data from a single time point (e.g., primary endpoint) as the main analysis method.

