6.3.2.2 Primary Efficacy Endpoint: Sensitivity Analyses

Sensitivity analyses of the primary efficacy endpoint (i.e., pain relief at 2 hours postdose during the DBT Phase) are provided in separate tables.

The RM=F method uses both criteria to classify subjects as failures (see Section 7.5).

Copy Reference Multiple Imputation

The main analysis is repeated using the copy reference multiple imputation approach with $n = 30$ imputations to impute missing headache pain intensity at 2 hours postdose. The fully conditional specification (FCS) method is used with a generalized logit distribution. Covariates may include history of clinically relevant CV disease randomization stratum (yes or no), sex, migraine headache pain intensity at the time of DB study drug dosing (moderate or severe), historical number of moderate to severe migraine attacks per month ($< \text{median}$, $\geq \text{median}$), MBS before DB study drug dosing (nausea, phonophobia, or photophobia), and geographic region (Australia/Europe or North America). First, the RM=F method of handling rescue medication use is applied. Next, missing response status (responder versus failure) in the 2-hour postdose analysis window is imputed for subjects who are not missing any of the covariates (subjects

missing any of the covariates are considered failures). The same statistics as the main analysis are presented, except “n/N”.

Varying Response Rate Imputation

The main analysis is repeated by imputing missing headache pain intensity at 2 hours postdose in each treatment group with varying response rates over the range of 0%, 10%, 20% and 30%. First, the RM=F method of handling rescue medication use is applied. Next, missing response status (responder versus failure) in the 2-hour postdose analysis window is imputed. The following statistics are presented: stratified percentage difference between treatment groups (rimegepant – placebo), ASE, 95% CI, and p-value.

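### The varying-response-rate analysis stops at 30%, below the plan's own 43.9% placebo rate, and does not say whether rates are crossed by arm, so it may miss the point where the primary result is lost

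*SAP*

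**What the plan says.** The main analysis of pain relief at 2 hours uses the NC=F rule in SAP 6.3: "Subjects with missing data at a single time point are classified as failures".

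SAP 6.3.2.2 adds two sensitivity analyses. One is copy reference multiple imputation with 30 imputations. The other, headed Varying Response Rate Imputation, first applies the rescue-medication rule and then fills in the remaining missing 2-hour responses "in each treatment group with varying response rates over the range of 0%, 10%, 20% and 30" percent. It reports the stratified difference, its standard error, the confidence interval and the p-value. It gives no reason for the 30% ceiling, does not say whether the rates in the two arms are crossed or equal, and does not list a tipping point as an output.

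SAP 5 bases the sample size on pooled Phase 3 response rates of "57.9% for rimegepant 75 mg and 43.9% for placebo in these studies".

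**The concern.** The main analysis already gives missing subjects a 0% response in both arms, so the 0%/0% cell of the new analysis repeats that missing-data rule. The added information comes from the other cells, above all those where missing placebo subjects do better than the main rule assumes.

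The grid ends 13.9 points below the planned placebo rate (43.9 − 30) and 27.9 points below the planned rimegepant rate (57.9 − 30). A missing placebo subject is therefore never given even the average placebo chance of relief. If significance would be lost at a rate above 30%, every cell in the report would be significant, and a reader could take the result as robust over a region that was not examined. The silence on crossing matters just as much, because it decides whether the analysis can challenge the result at all.

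**Working it through.** **Inputs.** From SAP 5: 270 evaluable per arm, response 57.9% vs 43.9%, two-sided alpha 0.05. From SAP 6.3.2.2: imputed rates 0%, 10%, 20%, 30%. Assumed: the share m per arm that is missing at 2 hours and not already a failure under the rescue rule. The documents give no figure, so a range is shown. The test is unstratified with unpooled standard error and ignores imputation variance. The planned rates are read as rates with missing counted as failure.

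**1. The plan's own figure.** The pooled rate is (0.579 + 0.439)/2 = 0.509.
- SE under the null = √(2 × 0.509 × 0.491/270) = 0.0430
- SE under the alternative = √((0.579 × 0.421 + 0.439 × 0.561)/270) = 0.0426
- Power = Φ((0.140 − 1.96 × 0.0430)/0.0426) = Φ(1.31) = 90.4%

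This agrees with the stated approximately 90%.

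**2. Same rate r in both arms, equal m.** The difference is (0.579 + m·r) − (0.439 + m·r) = 14.0 points for every r. At 10% missing, p stays at about 0.001 for r from 0% to 100%. This version cannot tip. With unequal missingness the difference does move: 5% missing on rimegepant, 20% on placebo and r = 30% gives 9.5 points, p = 0.026.

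**3. Crossed rates, rimegepant 0%, placebo q, planned 14-point difference.** The placebo rate becomes 0.439 + m·q. With rimegepant at 57.9%, z falls to 1.96 when the placebo rate reaches 49.5%: difference 0.0838, SE 0.0428. The tipping condition is therefore m·q ≈ 0.0562.
- q = 100%: m ≈ 5.6%
- q = 43.9%: m ≈ 0.0562/0.439 = 12.8%
- q = 30%: m ≈ 0.0562/0.30 = 18.7%

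| m per arm | p at q = 30% | p at q = 43.9% | p at q = 100% | tipping q (0.0562/m) |
|---|---|---|---|---|
| 5% | 0.003 | 0.006 | 0.035 | none |
| 8% | 0.007 | 0.014 | 0.16 | about 70% |
| 10% | 0.010 | 0.025 | 0.35 | about 56% |
| 15% | 0.026 | 0.083 | 0.81 (difference −1.0) | about 37% |
| 20% | 0.061 | 0.22 | 0.15 (difference −6.0) | about 28% |

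Below about 5.6% missing, no tipping point exists. From about 5.6% to 18.7%, one exists outside the grid. Above that, the grid reaches it.

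**4. Crossed rates, 10-point difference (53.9% vs 43.9%, p = 0.019).** The critical placebo rate is 45.5%, so m·q ≈ 0.0160. The grid tips once m exceeds 0.0160/0.30 = 5.3%. Between 1.6% and 5.3% missing, the tipping point lies outside it.
- 3% missing: p = 0.034 at q = 30% and 0.056 at q = 60%
- 5% missing: p = 0.047 at q = 30% and 0.069 at q = 43.9%
- 6% missing: p = 0.056 at q = 30%, so the planned grid already tips

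**5. Other reading of the planned rates.** If 57.9% and 43.9% are rates among subjects with data, 10% missing gives p = 0.025 at q = 30% and 0.055 at q = 43.9%.

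**The case against.** A reader might infer that the planned analysis can never show where the result is lost. The documents do not support that. If the arms are crossed, the grid tips at about 5.3% missing for a 10-point difference and about 18.7% for a 14-point difference. With little missing data at the planned effect there is nothing to find, and the ceiling does no harm.

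A reader might also take 43.9% as the rate that decides the matter. It does not: at the planned effect and 8% missing, 43.9% still gives p = 0.014, and the tipping rate is about 70%.

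The corner that drives these figures is deliberately severe. It pairs total failure among missing rimegepant subjects with relief among missing placebo subjects, in a blinded single-dose comparison. If missing subjects in both arms behaved like the observed ones, the difference would grow: at 5% missing, 10 points becomes 10/0.95 = 10.5 points (p = 0.014). This stands, and it is why a tipping point should come with a comment on plausibility.

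The copy reference imputation does bring in placebo-like rates. It brings them into both arms, however, so with equal missingness each arm gains about the same number of responders and the difference barely moves. It covers a different assumption and searches for no boundary.

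Finally, the SAP does not call this a tipping-point analysis, and Protocol 9.3.1.1 promises only that sensitivity analyses will be described in the SAP. No commitment is broken. SAP 6.3.1.2 also tabulates missing data by arm and time point, so readers can see the missing share, though not the boundary.

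**Conclusion.** The point holds as a gap in a sensitivity analysis. It is not a fault in the primary test or the sample size. The imputed rates stop below the plan's own placebo rate, and the text leaves open whether the arms vary independently. Under a common rate with equal missingness the analysis is uninformative. Under crossed rates it misses an existing tipping point for about 5.6% to 18.7% missing per arm at 14 points, and for about 1.6% to 5.3% at 10 points.

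These limits rest on assumed missing shares, equal in both arms, on 270 per arm, and on an unstratified test without imputation variance. The true missing share is unknown when the plan is written, so the plan should cover these ranges.

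**What to change.** In SAP 6.3.2.2, under Varying Response Rate Imputation:
- State that the imputed rates vary independently by arm.
- Run each arm from 0% to 100% in steps of 10%, and add each arm's observed rate.
- Report the boundary where p exceeds 0.05, or state that none exists, with a comment on how plausible the rates on that boundary are.

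A ceiling of 43.9% would not be enough, since the tipping rate can lie above it. The cost is SAP wording and a longer loop in an existing program. The downside is that reported robustness may look less favourable. The primary analysis, sample size and trial conduct do not change.

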6.3.3 Key Secondary Efficacy Endpoints

Key secondary efficacy endpoints are assessed using the DBT efficacy analysis set, unless specified otherwise. Results in Sections 6.3.3.1 through 6.3.3.10 support key secondary efficacy endpoints #1 through #10, respectively.

6.3.3.1 Pain Freedom at 2 Hours Postdose During the DBT Phase

Pain freedom at a single time point post dose is defined as having a migraine headache pain intensity of none at that time point.

The percentage of subjects with pain freedom at 2 hours postdose is compared between treatment groups using analogous methods as the main analysis of the primary endpoint with NC=F and RM=F (see Section 6.3.2.1). These results are presented together in the same table as those for pain freedom over time during the DBT Phase (see Section 6.3.5.1).

6.3.3.2 Rescue Medication Use Within 24 Hours Postdose During the DBT Phase

Analyses are based on the evaluable DBT efficacy analysis set, i.e., subjects in the DBT efficacy analysis set with first DBT rescue medication date \leq DB study drug date + 1 day and missing first DBT rescue medication time are excluded.

Time to first DBT rescue medication use is defined as (first DBT rescue medication date/time – DB study drug date/time) in hours (see Section 7.1). Rescue medication use within 24 hours postdose during the DBT Phase is defined as time to first DBT rescue medication use \leq 24 hours.

Treatment Group Comparisons

The percentage of subjects with rescue medication use within 24 hours postdose is compared between treatment groups using analogous methods as the main analysis of the primary endpoint, except that the NC=F and RM=F methods are not applied because they are not applicable to this endpoint (see Section 6.3.2.1).

Time to Rescue Medication Use Through 24 Hours Postdose

Time to rescue medication use through 24 hours postdose is assessed by treatment group as follows:

- Kaplan-Meier plot and table using 2-hour time intervals (i.e., 0 to ≤ 2 , >2 to ≤ 4 , ..., >24). The Kaplan-Meier plot displays the percentage of subjects taking rescue medication within 24 hours postdose on the y-axis versus time in hours on the x-axis.
- Time-to-event distribution table (hours).

See Section 6.1.1.1 for time-to-event plot and table attributes. Rescue medication use through 24 hours postdose is considered as an event in these time-to-event analyses. Subjects who do not take rescue medication within 24 hours postdose are censored at 24 hours and 1 minute (i.e., 1441 minutes).

6.3.3.3 Return to Normal Function at 2 Hours Postdose During the DBT Phase

Return to normal function at a single time point postdose is defined as a functional disability level of normal at that time point for the subset of subjects with functional disability at the time of dosing. Functional disability is defined as a functional disability level of mildly impaired, severely impaired, or requires bedrest. Thus, all analyses of return to normal function during the DBT Phase are based on the DBT efficacy analysis set with functional disability at the time of DB study drug dosing (see Section 7.5.2).

The percentage of subjects with return to normal function at 2 hours postdose during the DBT Phase is compared between treatment groups using analogous methods as the main analysis of the primary endpoint with NC=F and RM=F (see Section 6.3.2.1). These results are presented together in the same table as those for return to normal function over time during the DBT Phase (see Section 6.3.5.1).

6.3.3.4 Sustained Return to Normal Function From 2 to 24 Hours Postdose During the DBT Phase

Analyses are based on the DBT efficacy analysis set with functional disability at the time of DB study drug dosing.

Sustained return to normal function from 2 to 24 hours postdose is defined as a functional disability level of normal at all time points from 2 to 24 hours postdose.

Subjects who meet all the following criteria are classified as responders:

- Functional disability level of normal at all time points from 2 to 24 hours postdose, i.e., in the 2 to 24-hour postdose analysis windows
- Missing functional disability level at ≤ 1 time point from 3 to 8 hours postdose, i.e., in the 3, 4, 6, or 8-hour postdose analysis window
- No rescue medication taken at or before the functional disability level measurement in the 24-hour postdose analysis window (see Section 7.5).

Subjects who are not responders are classified as failures. Failure criteria include any of the following:

- Rescue medication taken at or before 24 hours postdose (RM=F; see Section 7.5)
- Functional disability level of mildly impaired, severely impaired, or requires bedrest at any time point from 2 to 24 hours postdose, i.e., in the 2, 3, 4, 6, 8 or 24-hour postdose analysis window
- Missing functional disability measurement at 2 or 24 hours postdose (NC=F), i.e., in the 2 or 24-hour postdose analysis window
- Missing functional disability measurement at >1 time point from 3 to 8 hours postdose (NC1=F), i.e., in the 3, 4, 6, or 8-hour postdose analysis window.

The percentage of subjects with sustained return to normal function from 2 to 24 hours postdose during the DBT Phase is compared between treatment groups using analogous methods as the main analysis of the primary endpoint with NC=F, NC1=F, and RM=F (see Section 6.3.2.1). These results are presented together in the same table as those for sustained return to normal function from 2 to 48 hours postdose during the DBT Phase (see Section 6.3.3.5).

6.3.3.5 Sustained Return to Normal Function From 2 to 48 Hours Postdose During the DBT Phase

Analyses are based on the DBT efficacy analysis set with functional disability at the time of DB study drug dosing.

Sustained return to normal function from 2 to 48 hours postdose is defined as a functional disability level of normal at all time points from 2 to 48 hours postdose.

Subjects who meet all the following criteria are classified as responders:

- Functional disability level of normal at all time points from 2 to 48 hours postdose, i.e., in the 2 to 48-hour postdose analysis windows
- Missing functional disability level at ≤1 time point only from 3 to 8 hours postdose, i.e., in the 3, 4, 6, or 8-hour postdose analysis window
- No rescue medication taken at or before the functional disability level measurement in the 48-hour postdose analysis window (see Section 7.5).

Subjects who are not responders are classified as failures. Failure criteria include any of the following:

- Rescue medication taken at or before 48 hours postdose (RM=F; see Section 7.5)
- Functional disability level of mildly impaired, severely impaired, or requires bedrest at any time point from 2 to 48 hours postdose, i.e., in the 2, 3, 4, 6, 8, 24, or 48-hour postdose analysis window
- Missing functional disability measurement at 2, 24, or 48 hours postdose (NC=F), i.e., in the 2, 24, or 48-hour postdose analysis window

- Missing functional disability measurement >1 time point from 3 to 8 hours postdose (NC1=F), i.e., in the 3, 4, 6, or 8-hour postdose analysis window.

The percentage of subjects with sustained return to normal function from 2 to 48 hours postdose during the DBT Phase is compared between treatment groups using analogous methods as the main analysis of the primary endpoint with NC=F, NC1=F, and RM=F (see Section 6.3.2.1). These results are presented together in the same table as those for sustained return to normal function from 2 to 24 hours postdose during the DBT Phase (see Section 6.3.3.4).

6.3.3.6 Sustained Pain Relief From 2 to 24 Hours Postdose During the DBT Phase

Sustained pain relief from 2 to 24 hours postdose is defined as migraine headache pain intensity of none or mild at all time points from 2 to 24 hours postdose.

Subjects who meet all the following criteria are classified as responders:

- Migraine headache pain intensity of none or mild at all time points from 2 to 24 hours postdose, i.e., in the 2 to 24-hour postdose analysis windows
- Missing migraine headache pain intensity at ≤1 time point only from 3 to 8 hours postdose, i.e., in the 3, 4, 6, or 8-hour postdose analysis window
- No rescue medication taken at or before the migraine headache pain intensity measurement in the 24-hour postdose analysis window (see Section 7.5).

Subjects who are not responders are classified as failures. Failure criteria include any of the following:

- Rescue medication taken at or before 24 hours postdose (RM=F; see Section 7.5)
- Moderate or severe migraine headache pain intensity at any time point from 2 to 24 hours postdose, i.e., in the 2, 3, 4, 6, 8, or 24-hour postdose analysis window
- Missing migraine headache pain intensity at 2 or 24 hours postdose (NC=F), i.e., in the 2 or 24-hour postdose analysis window
- Missing migraine headache pain intensity at >1 time point from 3 to 8 hours postdose (NC1=F), i.e., in the 3, 4, 6, or 8-hour postdose analysis window.

The percentage of subjects with sustained pain relief from 2 to 24 hours postdose during the DBT Phase is compared between treatment groups using analogous methods as the main analysis of the primary endpoint with NC=F, NC1=F, and RM=F (see Section 6.3.2.1). These results are presented together in the same table as those for sustained pain relief from 2 to 48 hours postdose during the DBT Phase (see Section 6.3.3.7).

6.3.3.7 Sustained Pain Relief From 2 to 48 Hours Postdose During the DBT Phase

Sustained pain relief from 2 to 48 hours postdose is defined as migraine headache pain intensity of none or mild at all time points from 2 to 48 hours postdose.

Subjects who meet all the following criteria are classified as responders:

- Migraine headache pain intensity of none or mild at all time points from 2 to 48 hours postdose, i.e., in the 2 to 48-hour postdose analysis windows
- Missing migraine headache pain intensity at ≤ 1 time point only from 3 to 8 hours postdose, i.e., in the 3, 4, 6, or 8-hour postdose analysis window
- No rescue medication taken at or before the migraine headache pain intensity measurement in the 48-hour postdose analysis window (see Section 7.5).

Subjects who are not responders are classified as failures. Failure criteria include any of the following:

- Rescue medication taken at or before 48 hours postdose (RM=F; see Section 7.5)
- Moderate or severe migraine headache pain intensity at any time point from 2 to 48 hours postdose, i.e., in the 2, 3, 4, 6, 8, 24, or 48-hour postdose analysis window
- Missing migraine headache pain intensity at 2, 24, or 48 hours postdose (NC=F), i.e., in the 2, 24, or 48-hour postdose analysis window
- Missing migraine headache pain intensity at >1 time point from 3 to 8 hours postdose (NC1=F), i.e., in the 3, 4, 6, or 8-hour postdose analysis window.

The percentage of subjects with sustained pain relief from 2 to 48 hours postdose during the DBT Phase is compared between treatment groups using analogous methods as the main analysis of the primary endpoint with NC=F, NC1=F, and RM=F (see Section 6.3.2.1). These results are presented together in the same table as those for sustained pain relief from 2 to 24 hours postdose during the DBT Phase (see Section 6.3.3.6).

6.3.3.8 Sustained Pain Freedom From 2 to 24 Hours Postdose During the DBT Phase

Sustained pain freedom from 2 to 24 hours postdose is defined as migraine headache pain intensity of none at all time points from 2 to 24 hours postdose.

Subjects who meet all the following criteria are classified as responders:

- Migraine headache pain intensity of none at all time points from 2 to 24 hours postdose, i.e., in the 2 to 24-hour postdose analysis windows
- Missing migraine headache pain intensity at ≤ 1 time point only from 3 to 8 hours postdose, i.e., in the 3, 4, 6, or 8-hour postdose analysis window

- No rescue medication taken at or before the migraine headache pain intensity measurement in the 24-hour postdose analysis window (see Section 7.5).

Subjects who are not responders are classified as failures. Failure criteria include any of the following:

- Rescue medication taken at or before 24 hours postdose (RM=F; see Section 7.5)
- Mild, moderate, or severe migraine headache pain intensity at any time point from 2 to 24 hours postdose, i.e., in the 2, 3, 4, 6, 8, or 24-hour postdose analysis window
- Missing migraine headache pain intensity at 2 or 24 hours postdose (NC=F), i.e., in the 2 or 24-hour postdose analysis window
- Missing migraine headache pain intensity at >1 time point from 3 to 8 hours postdose (NC1=F), i.e., in the 3, 4, 6, or 8-hour postdose analysis window.

The percentage of subjects with sustained pain freedom from 2 to 24 hours postdose during the DBT Phase is compared between treatment groups using analogous methods as the main analysis of the primary endpoint with NC=F, NC1=F, and RM=F (see Section 6.3.2.1). These results are presented together in the same table as those for sustained pain freedom from 2 to 48 hours postdose during the DBT Phase (see Section 6.3.3.9).

6.3.3.9 Sustained Pain Freedom From 2 to 48 Hours Postdose During the DBT Phase

Sustained pain freedom from 2 to 48 hours postdose is defined as migraine headache pain intensity of none at all time points from 2 to 48 hours postdose.

Subjects who meet all the following criteria are classified as responders:

- Migraine headache pain intensity of none at all time points from 2 to 48 hours postdose, i.e., in the 2 to 48-hour postdose analysis windows
- Missing migraine headache pain intensity at ≤1 time point only from 3 to 8 hours postdose, i.e., in the 3, 4, 6, or 8-hour postdose analysis window
- No rescue medication taken at or before the migraine headache pain intensity measurement in the 48-hour postdose analysis window (see Section 7.5).

Subjects who are not responders are classified as failures. Failure criteria include any of the following:

- Rescue medication taken at or before 48 hours postdose (RM=F; see Section 7.5)
- Mild, moderate, or severe migraine headache pain intensity at any time point from 2 to 48 hours postdose, i.e., in the 2, 3, 4, 6, 8, 24, or 48-hour postdose analysis window
- Missing migraine headache pain intensity at 2, 24, or 48 hours postdose (NC=F), i.e., in the 2, 24, or 48-hour postdose analysis window

- Missing migraine headache pain intensity at >1 time point from 3 to 8 hours postdose (NC1=F), i.e., in the 3, 4, 6, or 8-hour postdose analysis window.

The percentage of subjects with sustained pain freedom from 2 to 48 hours postdose during the DBT Phase is compared between treatment groups using analogous methods as the main analysis of the primary endpoint with NC=F, NC1=F, and RM=F (see Section 6.3.2.1). These results are presented together in the same table as those for sustained pain freedom from 2 to 24 hours postdose during the DBT Phase (see Section 6.3.3.8).

